Participants will wear an activity monitor for one week per month. This will allow us to collect average physical activity across one week time periods which will be used to analyze the impact of the intervention outside of the structured exercise sessions of the endurance exercise group. This will allow us to determine if the endurance exercise group alters its overall activity level over the 6 month time period.

- c) Change from baseline to 6-months for brain imaging measures including the following:
- 1) Hippocampal volumes on structural MRI,
 - 2) Microstructural integrity of white matter pathways on diffusion tensor imaging (DTI),
 - 3) Functional connectivity among brain networks on resting state fMRI,
 - 4) Responses to task-based fMRI Digit Symbol Substitution Test.
- d) Change from baseline to 6-months for biospecimen measures including the following:
- 1) Salivary cortisol measurements; in addition, changes in salivary cortisol measures collected over 8 time points on two consecutive days will be explored at the pre-test and the post-test. We will measure cortisol at time points 0 minutes, 15 minutes, 30 minutes, 45 minutes after the person wakes up.(Stalder, Kirschbaum et al. 2016) In addition, we will measure cortisol at 3 hours, 6 hours, 9 hours and 12 hours after awakening.(Edwards, Clow et al. 2001)
 - 2) Soluble inflammatory biomarkers in plasma
 - 3) Peripheral levels of neurotrophic factors in plasma

PROTOCOL TITLE: Mild Cognitive Impairment and Endurance Exercise in Parkinson's Disease

e) We will collect the NINDS common data elements (CDE) for sex, ethnicity, date-of-birth, education level, family history, and employment status.

- 8.2. Safety Endpoints: There are no safety endpoints, but all participants will be monitored for safety and for adverse events.

Adverse Events (AEs) are defined as exercise-related discomforts (e.g., muscle and joint soreness/pain), minor injuries (e.g., strains, sprains), and non-injurious falls; and attrition is defined as the number of participants who withdraw from the study. Serious Adverse Events (SAEs) are defined as hospitalization, surgery, death, or permanent disability. We will keep detailed logs of all the training sessions so that we can monitor their progress in the endurance exercise program and assess compliance, which we will take to be completion of 80% of the prescribed exercise sessions.

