11.0 Data and Specimen Management

- 11.1* We are collecting pilot data primarily for feasibility, though statistical analyses may be conducted to provide descriptive data of the subject cohort, baseline and 6-month test scores, and potentially exploratory analyses of change in outcome measures or correlations of variables.
- 11.2* Since we are collecting pilot data, there is no power analysis.

PROTOCOL TITLE: Mild Cognitive Impairment and Endurance Exercise in Parkinson's Disease

- 11.3* The research will be conducted in compliance with state and federal laws, including the Health Insurance Portability and Accountability Act (HIPAA) that require researchers to protect and maintain confidentiality of an individual's health information. All subjects will be asked to sign an "Authorization To Use and Disclose (Release) Health Information For a Research Study". Access to all study datasets will be password protected. All research staff will be trained in proper research procedures. We have extensive experience in data capture, data flow and data management based on our SPARX Phase II clinical trial.(Moore, Schenkman et al. 2013) We will use REDCap (Research Electronic Data Capture) to define and manage our own data collection forms. This service is provided through the Northwestern University Clinical and Translational Institute.
- 11.4* Quality control is addressed at the point of data collection, data entry, and data analysis.
- Imaging – the imaging center conducts tests for quality control of the imaging data. A quality control scan is run every day before data acquisition begins.
 - All of our data is double checked for accuracy by a member of our research team. Periodically we have our data checked by a person who is not directly involved in the laboratory.
- 11.5* Study-wide handling of data and specimens is described below:
- Our data consists of analog data and text.
 - Our data is stored on hard disks and backed up regularly.
 - Our data is stored indefinitely.
 - The clinical coordinator, statistician and students and post- doctoral fellows will have access to the data.
 - The clinical coordinator is responsible for receipt of the data.
 - The data will not be transported.
 - The cortisol data will initially stored in a freezer at -80°C before being shipped out for analysis.

12.0 Provisions to Monitor the Data to Ensure the Safety of Subjects:

This study does not involve more than minimal risk.

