13.0 Withdrawal of Subjects*

- 13.1* Participation in this study will be stopped by the investigator without subject consent if circumstances arise which warrant doing so. This would include injury that would limit participation in the exercise portion of the study or if the person became ill during the research, they may have to drop out, even if they would like to continue. The investigators, [name] and [name]. will make the decision and let the person know if it is not possible

PROTOCOL TITLE: Mild Cognitive Impairment and Endurance Exercise in Parkinson's Disease

for them to continue. The decision may be made to protect the health and safety of the participant.

13.2 Subjects may withdraw for the research at any time point. Subjects will be asked if they would be willing to take part in the post-test.

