14.0 Risks to Subjects*

14.1 Overall, potential foreseeable risks associated with participation in the study are very unlikely and of low risk.

- The potential risks of endurance exercise includes injury to tendons, ligaments, joints, and muscles. There is little likelihood of any physical risk as a result of participation in this research project. The exercise and testing procedures have been well established for people with Parkinson's disease. The use of a well-trained personal trainer further reduces any possible risks.
- During exercise testing there is a chance that subjects could fall, feel pain in their muscles or joints, feel dizzy or faint, have irregular heartbeats, have a stroke or heart attack, or die. The risk of death from an exercise stress test has been estimated to be 1 in 100,000. The risk of a heart attack is about 4 in 10,000 and the risk of a problem that would require hospitalization (for example, chest pain) is about 2 in 1,000. To minimize this risk, only subjects at low to moderate risk will be allowed to participate in exercise testing. Subjects can request to terminate the exercise test at any point during testing. ACSM subject screening and testing guidelines will be followed. The exercise test will be administered by an exercise physiologist who is Advanced Cardiac Life Support (ACLS) certified and has automated external defibrillator (AED) experience. The exercise physiologist administering the test will also have knowledge of appropriate contraindications, risk, and risk assessment of testing, the absolute and relative indications for termination of the exercise test, knowledge of cardiac arrhythmias, and the ability to recognize and treat serious arrhythmias if they arise.
- There are no known hazards to diffusion magnetic resonance imaging, functional magnetic resonance imaging, other than the discomfort associated with confinement and remaining stationary for the duration of the testing procedure. We have found that training in the MR simulation scanner helps to reduce the stress associated with the noise and confinement of the actual MR scanner environment. Testing of all participants will be terminated immediately should they become distressed. We will carefully screen out individuals who have an implanted electrical device (such as a cardiac pacemaker or a neurostimulator), or a certain type of metallic clip (i.e., an aneurysm clip

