PROTOCOL TITLE: Mild Cognitive Impairment and Endurance Exercise in Parkinson's Disease

in the brain). These devices can malfunction and cause harm to the patient in the magnet environment. We will also carefully screen individuals who are claustrophobic to reduce any adverse events. We anticipate that most patients will come by limousine to the testing facility when off medication. Under no circumstance will we allow a patient to drive when off medication.

- Risk associated with blood draws: pain, a bruise at the point where blood is taken, redness and swelling of the vein and infection, and a rare risk of fainting. These risks associated with blood draws are minimal, and are reduced in this study because trained personnel who have extensive venipuncture experience, and are trained in aseptic technique, will implement the blood drawing procedures in a clean room.

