26.0 Compensation for Research-Related Injury

- 26.1 Minimal risk is when the probability and magnitude of harm or discomfort anticipated in the proposed research are not greater, in and of themselves, than those ordinarily encountered in daily life or during the performance of routine physical or psychological examinations or tests. The proposed research does not exceed minimal risk. In the event of research-related injury, subjects will not be compensated for medical care required because of an untoward outcome resulting from participation in the research study. Subjects should seek medical treatment through his or her doctor or treatment center of choice.
- 26.2 If a participant becomes ill or get an injury or illness as a result of study (medications, devices or procedures), they should seek medical treatment through their doctor or treatment center of choice. They should promptly tell the study doctor about any illness or injury. The hospital [university, researchers] will not pay for medical care required because of a bad outcome resulting from their participation in this research study. This does not keep them from seeking to be paid back for care required because of a bad outcome.

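### Section 8.2 defines adverse events by three mild types and serious ones by four outcomes, so a more-than-minor injury or a procedure-related event with no serious outcome is in neither class

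*Combined protocol and SAP*

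**What the plan says.** Section 8.2 sets no safety endpoint but says that participants will be monitored for safety and for adverse events. It then gives three definitions:

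- Adverse events: "Adverse Events (AEs) are defined as exercise-related discomforts (e.g., muscle and joint soreness/pain), minor injuries (e.g., strains, sprains), and non-injurious falls".
- Serious adverse events: "Serious Adverse Events (SAEs) are defined as hospitalization, surgery, death, or permanent disability".
- Attrition: "attrition is defined as the number of participants who withdraw from the study".

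Table 1 in Section 9.4 schedules AE/SAE collection and attrition each month and adds nothing to the definitions. Section 12.0, the place for safety monitoring provisions, says only: "This study does not involve more than minimal risk".

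Other sections foresee harms without assigning them to a class:

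- Section 14.1, on training: "The potential risks of endurance exercise includes injury to tendons, ligaments, joints, and muscles". On exercise testing, it also names dizziness or faintness and irregular heartbeats.
- Section 14.1, on the blood draw, includes "redness and swelling of the vein and infection, and a rare risk of fainting".
- Section 13.1, on circumstances in which the investigator stops participation: "This would include injury that would limit participation in the exercise portion of the study or if the person became ill during the research".
- Section 26.2, on what participants are asked to do: "They should promptly tell the study doctor about any illness or injury".

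**The concern.** The two lists leave a gap in the middle of the severity scale. The AE list stops at minor injuries and falls without injury; the SAE list begins at hospital admission. Between them lies the injury that is treated without admission or operation and heals, but is worse than a strain or sprain. A definition that counts soreness and omits this event does not rank harms sensibly.

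The AE list is also built around exercise, while the study includes a maximal exercise test and blood draws with risks of their own.

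The stake is what the pilot can say about harm. Section 2.2 says that the data are to support a subsequent R01, and Section 11.1 says that they are collected mainly for feasibility. Whether people stop because the programme hurt them is a central feasibility question. Under 8.2 as written, one such person can appear as one withdrawal and no adverse event.

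**Working it through.** No figure in the protocol depends on these definitions, so there is none to reproduce. The check sets each foreseeable event against the two lists in 8.2. The examples in brackets in the AE definition are open within each type, but the set of types has no clause for other events.

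| Event | AE list | SAE list | Result as written |
|---|---|---|---|
| Muscle or joint soreness, strain, sprain | yes | no | counted |
| Fall without injury | yes | no | counted |
| Fall with a minor injury | yes, as a minor injury | no | counted |
| More-than-minor injury, from a fall or otherwise, with none of the four SAE outcomes (training injury foreseen in 14.1) | no | no | neither class |
| Blood-draw infection, no SAE outcome (14.1) | no | no | neither class |
| Faint without a fall, no SAE outcome (14.1) | no | no | neither class |
| Faint with a harmless fall | yes, as a fall without injury | no | counted |
| Irregular heartbeat at exercise testing, no SAE outcome (14.1) | no | no | neither class |
| Dizziness at exercise testing, no SAE outcome (14.1) | arguable | no | depends on the reader |
| Any event with an SAE outcome | not needed | yes | counted |

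Two rows need judgement. Dizziness on the treadmill might pass as an exercise-related discomfort, although the examples given are musculoskeletal. A bruise from the blood draw, not shown, might pass as a minor injury.

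Next, withdrawal. Section 13.1 foresees injury or illness ending participation. If that event fits neither list, the only tally that 8.2 requires is attrition, which is defined as a number. No section requires a reason to be recorded with it.

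Direction: an event outside both lists adds 0 to the harm count, where a general definition would add 1. The count can fall short but cannot be inflated by this route.

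Size: the documents give no rate for these events, so the number missed cannot be computed. The effect of one affected person on the proportion with any AE can be bounded. With all 16 participants enrolled, it is 1/16 = 6.25 percentage points if that person has no other AE, and 0 if that person also reports, say, soreness. In the second case the proportion is unchanged, but the event and its severity are lost.

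**The case against.** The strongest reply has four parts.

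**The term is used more widely elsewhere.** Section 9.3 speaks of hand pain or other adverse events during testing, and Section 14.1 uses the term for claustrophobia in the scanner. This suggests that the authors would treat procedure-related harms as adverse events. It is fair evidence of intent, but neither passage redefines the term, and 8.2 is where the definition stands.

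**Not classed does not mean not recorded.** A reader might infer that these events would vanish from the data. The documents do not show that. The investigators decide on stopping for injury or illness and so know the reason, participants are asked to report any illness or injury, sessions are logged, and adherence is checked weekly. The forms listed in Section 9.3 are those for test measures, so their silence on an AE form proves nothing. What stands is narrower: staff may record more, but the plan does not require it, so the tally would depend on individual practice.

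**Leaving out ordinary illness is a scoping choice.** A reader might infer that the plan is wrong because it does not capture every illness. These documents set no such standard, and a small study without a control group may reasonably limit its scope to exercise and study procedures. This part of the reply holds. It does not cover injuries, falls or procedure-related events, which fall within any sensible scope.

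**No inference depends on it.** This is correct: there is no safety endpoint and, by Section 11.2, no power analysis.

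**Conclusion.** The gap is real and worth fixing, but limited. As written, 8.2 gives no class to a more-than-minor injury, from a fall or otherwise, or to several procedure-related events that the protocol foresees, when none of the four SAE outcomes follows. The resulting descriptive harm count can only be too low. No endpoint, sample size or error rate changes.

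The conclusion rests on reading the three AE types as a complete list, which the wording supports, and on there being no wider definition in the text available. It does not rest on any assumed event rate.

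A reader might infer that every faint or blood-draw problem goes uncounted. That is too broad: a faint with a harmless fall is already an AE, and any event leading to admission is an SAE. A reader might also try to size the problem from the number of sessions or the share done off site. Those are exposures, not events, and do not bear on the definition. Moreover, the Exercise Intervention text in Section 9.2 and Sections 19.1 and 21.1 differ on where early training takes place.

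**What to change.** In Section 8.2, define an adverse event as any untoward medical occurrence during participation. If a narrower scope is preferred, state it, and include at least any injury, any fall, and any event related to exercise or to a study procedure. Define serious adverse events as the subset that meets the four outcomes already listed, and report the rest as non-serious. Keep the three present types as subcategories.

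Count all falls, with the level of injury. For each event record severity and relatedness to exercise or to a study procedure. For each withdrawal record the reason. Check the new wording against the events named in Sections 13.1 and 14.1.

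The cost is one paragraph and a few fields at the monthly AE/SAE and attrition collection already in Table 1, unless the existing forms already hold them. Somewhat more events will be recorded, some unrelated to exercise. As the protocol describes no control group, related and unrelated events should be tabulated separately. No visit, intervention, endpoint or sample size changes.

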9.0 Procedures Involved

- 9.1 We will conduct a single coordination site, blinded-evaluator, open-label, intervention study of the effects of 6 months of high intensity endurance exercise on cognitive and other clinical/behavioral measures, brain imaging, and cortisol and blood specimens. These measures will be collected at baseline and then again at 6-months or at an early termination visit, should that occur. Cortisol will be collected twice at baseline on consecutive days and twice at 6 months on consecutive days. Blood will be drawn both at baseline and again at 6 months.
- 9.2 The research procedures and when they are performed are explained below.

Telephone Screening

Telephone screening will occur after referral by the Neurologist. The subject will learn about the study. The screen will rule out any medical conditions that preclude participation in endurance exercise training, brain MRI imaging, or behavioral testing. The screening will last approximately 30 minutes. None of the information attained from the screening will be recorded or utilized as research data. The screening will take place prior to scheduling the subject for any study related data collection and prior to consenting to take part in the research study. If the subject passes the telephone screening, they will be scheduled to come in for testing.

Baseline Visit

PROTOCOL TITLE: Mild Cognitive Impairment and Endurance Exercise in Parkinson's Disease

Day 1 Afternoon

Obtain written consent and written HIPAA authorization. We will collect NINDS common data elements for sex, ethnicity, date-of-birth, education level, PD disease history, medication history, family history, and employment status from all subjects. In addition, Movement Disorder Society-Unified Parkinson Disease Rating Scale (MDS-UPDRS) Part I, II, and IV of the MDS-UPDRS, and non-motor rating scales will be administered.

1. Informed consent and HIPAA Authorization – 20 minutes to complete
2. SCOPA-Cog – 15 minutes
3. NINDS common data elements – 20 minutes
4. MDS-UPDRS
 - a. Part IA completed by rater – 10 minutes to administer
 - b. Part IB questionnaire completed by patient – 5 minutes to complete
 - c. Part II questionnaire completed by patient – 5 minutes to complete
 - d. Part IV completed by rater – 5 minutes to administer
5. Montreal Cognitive Assessment – 10 minutes to complete
6. Pittsburgh Sleep Quality Index – 7 minutes to complete
7. Epworth Sleepiness Scale – 7 minutes to complete
8. Fatigue Severity Scale – 7 minutes to complete
9. Hamilton Depression Scale – 10 minutes to complete
10. PD Neurol QOL – 10 minutes to complete
11. PDQ-39 Scale– 10 minutes to complete
12. Maximal graded exercise test – 1 hour to complete
 - A maximal graded exercise test (GXT) will be performed during intake day to determine HRmax. A resting 12-lead ECG will be recorded in the recumbent and upright positions immediately prior to the exercise test, as well as during the test. If the findings on the resting ECG do not contraindicate exercise, the exercise test will be performed.
 - Contraindicators include the following: (a) ST-segment depression of more than 0.2 mV that is either horizontal, downsloping, or slowly upsloping (less than 1 mV/sec) and lasts for 0.08 sec, or ST-segment elevation greater than 0.1 mV; (b) chest pain or discomfort; (c) serious arrhythmias, including multifocal PVCs, ventricular tachycardia, frequent (>10/min) PVCs or couplets, or sustained atrial tachyarrhythmias; (d) A-V block or other conduction defects; (e) a fall of systolic blood

PROTOCOL TITLE: Mild Cognitive Impairment and Endurance Exercise in Parkinson’s Disease

pressure of 10 mmHg or greater from the peak level with increasing exercise intensity; (f) diastolic blood pressure above 110 mmHg or systolic above 220 mmHg; (g) dizziness; (h) ataxic gait; and (i) pallor or cyanosis. Subjects who have a positive GXT will be ineligible for participation in the study.

- Maximal aerobic power (VO2max) will be measured by indirect calorimetry (TruMax 2400, ParvoMedics, Sandy, UT) during the GXT. A warm-up period on the treadmill will be used to identify the walking speed that generates a HR that is 65-70% of the age-predicted HRmax; for fit individuals, this may require increasing the elevation of the treadmill. After a brief rest interval to initiate the indirect calorimetry, the test will start at the designated walking speed (and grade). The treadmill grade will be increased by 2% every 2 minutes to volitional exhaustion or until the proctor stops the test because of abnormal responses to exercise.

Night Before Testing:

Last dose of antiparkinsonian medications no later than 8.30pm.

Last coffee and alcohol no later than 8.30 pm

Day 2:

Imaging 8:30 to 10:00 AM

MRI Data Acquisition

MRI data will be acquired using a state-of-the-art Prisma 3.0T whole-body clinical MRI system equipped with a high performance gradient system capable of on-axis (x, y and z) peak gradient of ≥ 80 mT/m and 200 mT/m/ms slew rate, and a 64-channel head coil. The scanner is capable of implementing the Human Connectome Protocol (HCP) like sequences. The imaging protocols are designed for one-hour sessions, which in our extensive experience has been well tolerated by all types of PD patients. A headphone, which is a component of the dedicated task delivery system (Avotec system for the standard coil and earbuds from Sensimetrics for 64 channel coils), will be placed over the participant’s ears for operator-participant communication. Video stimuli will be delivered through a rear projection system at Northwestern. The fMRI task is described below.

Scan#	Preferred Order NU	Scan Time (min:sec)	Total Time	Total Scan Time
0	Setup	10:00:00	10 min	0 min
1	Scout	0:14:00	10 min 14 sec	0 min 14 sec
2	T 1	4:22:00	14 min 36 sec	4 min 36 sec
3	T 2	3:52:00	18 min 28 sec	8 min 28 sec

PROTOCOL TITLE: Mild Cognitive Impairment and Endurance Exercise in Parkinson's Disease

4	Resting fMRI – MB8 A>>P	8:08:00	26 min 36 sec	16 min 36 sec
5	Resting fMRI – MB8 P>>A	0:14:00	26 min 50 sec	16 min 50 sec
6	BO field mapping	2:15:00	29 min 05 sec	19 min 05 sec
7	Diffusion (NODDI) AP	10:52:00	39 min 57 sec	29 min 57 sec
8	Diffusion (NODDI) PA	0:33:00	40 min 30 sec	30 min 30 sec

MRI Imaging Session

Scan #1. Auto-Align Scout (Scout, 12 seconds): A single low resolution structural scout scan is collected in the sagittal orientation (TR/TE/flip angle = 3.15 ms/1.37 ms/8°, GRAPPA factor = 3, 1.6 mm isotropic voxels, 128 contiguous slices). The imaging parameters are chosen to obtain a low resolution image which can be used for planning purposes.

Scan #2. T1w structural MRI (MPRAGE, 4 minutes 22 seconds): Volumetric/structural images are obtained using a high resolution three-dimensional (3D) T1-weighted (T1WI) fast gradient echo sequence (TR/TE/flip angle = 2000ms/2.99ms/8°, TI=900 ms, GRAPPA = 2, Partial Fourier = 6/80.8 mm isotropic voxels, 208 contiguous slices). The imaging parameters are chosen to obtain excellent contrast among gray matter, white matter, and cerebral spine fluid (CSF).

Scan #3. T2w structural MRI (3 minutes 52 seconds): Volumetric/structural images are obtained using a high resolution three-dimensional (3D) T2-weighted (T2WI) fast gradient echo sequence (TR/TE = 2500ms/370ms, GRAPPA = 3, 0.8mm isotropic voxels, 208 contiguous slices). The purpose of this scan is to delineate T2 lesions and assist in coregistration and alignment.

Scan #4, and #5. Resting state BOLD fMRI (2 separate resting state scans, 8 minutes and 8 seconds and 14 seconds): Whole brain activation fMRI is obtained with a single-shot gradient echo EPI sequence sensitized to BOLD effect (TR/TE/flip angle = 613ms/22ms/47°, 2mm isotropic voxels, 72 interleaved slices, zero gap). Multiband technology is utilized to speed up data acquisition (MB = 8). The participant is instructed to focus his/her vision on the fixation point (a cross) on the screen, and try to keep their minds free of thought.

Scan #6. B0 field mapping (2 minutes 15 seconds): A dual-echo fast 3D gradient echo sequence is run to map the B0 field (TR/TE1/TE2/flip angle = 733ms/4.92ms/7.38ms/50°, 2mm isotropic voxels, 72 contiguous slices).

Scan #7. and #8 dMRI (NODDI) scan (2 separate scans, 10 minutes 52 seconds and 33 seconds): Whole brain diffusion MRI is obtained with a single-shot spin echo EPI sequence sensitized to diffusion effect (TR/TE/flip angle = 3200ms/70ms/90°/180°, 2.0 mm isotropic voxels, 69 interleaved

PROTOCOL TITLE: Mild Cognitive Impairment and Endurance Exercise in Parkinson's Disease

slices, zero gap. 64 directions are collected for $b=1000$, $b=2000$ and $b=3000$ s/mm^2), including 5 $b = 0$ (1 at the beginning and 4 at the end of the scan). Multiband technology is utilized to speed up data acquisition (MB = 3) along with GRAPPA = 2.

Blood draw – 15 minutes to complete

- 30 mL of blood will be taken via antecubital blood draw by a trained nurse from the Clinical Research Unit. Blood will be collected into 10mL K2EDTA tubes (3 per subject) to collect plasma. Blood will be centrifuged at 100-1300RCF for 10min before plasma is collected and transferred to 500ul aliquots. Plasma will be stored at -80 degrees until it is shipped on dry ice to [name] at Emory University. Half of the samples from each participant will be shipped to Emory University, while the other half will stay stored at the Clinical Research Unit as a back up, in case for any reason something happens to the shipment. Both the samples shipped to Emory University and stored in the Clinical Research Unit will be coded using subject study code numbers and will not contain any identifiable subject information. At Emory University, plasma will be subjected to multiplexed immunoassay for measurement of soluble inflammatory markers and neurotrophic factors. Emory University will destroy the samples following analysis. The Clinical Research Unit will destroy the back up samples left behind once they have received written authorization to do so from our research staff, which will happen as soon as the shipped samples are analyzed.

Behavioral testing session 1: (10:30 to 11:30)

Pending subject consent, some of the following behavioral tests may be video or audio recorded to aid in data analysis.

- 1) MDS-UPDRS, PART III, Motor Section: to measure PD disease severity – 15 minutes to administer
- 2) Mini Balance Evaluation Systems Test – 10 minutes to administer
- 3) Timed up and Go (3 trials) - 3 minutes to administer
- 4) Six-minute walk test – 7 minutes to administer
- 5) Activities-Specific Balance Confidence Scale – 15 minutes to administer
- 6) New Freezing of Gait Questionnaire – 10 minutes to administer

Testing is over for the day.

The last dose of antiparkinsonian medications is taken no later than 8.30pm.

PROTOCOL TITLE: Mild Cognitive Impairment and Endurance Exercise in Parkinson's Disease

Last coffee and alcohol no later than 8.30 pm.

Days 3:

Behavioral testing session 2: (8:30 to 10:25)

Pending subject consent, some of the following behavioral tests may be video or audio recorded to aid in data analysis.

Cognitive testing:

1. Montreal Cognitive Assessment, alternate version – 10 minutes to complete
2. Symbol Digit Modality Test – 5 min to complete
3. Trail Making Test-Parts A and B – 10 min to complete
4. Raven's Progressive Matrices — 10 min to complete
5. Clock Drawing/copying – 10 min to complete
6. Hopkins HVLT-R Word list learning, delayed recall and recognition – 10 min to complete
7. Free and Cued Selective Reminding Test, delayed recall and recognition – 15 min to complete
8. Figural memory test - to measure visual memory – 10 min to complete
9. Boston Naming Test (15 item) - 5 min to complete
10. Verbal fluency [semantic - animals, phonemic - letters] – 5 min to complete
11. Judgment of Line Orientation (15 item) - 10 min to complete
12. Intersecting pentagons – 5 min to complete

Day 4 and Day 5 (These will be 2 typical week days):

Cortisol Assessment

We will collect saliva samples during the post-awakening period (0, 15, 30, and 45 minutes post-awakening) to measure the cortisol awakening response. We will also collect samples at approximately (3, 6, 9 and 12 hours post-awakening) on two consecutive weekdays. The participant will be required to record and report their awakening and saliva sampling times. There will be objective measurement of awakening and sampling times in the 45 minutes post awakening.

Exercise Intervention

Intervention, Administration and Duration

Subjects will exercise on a treadmill using procedures that have been used over the past two decades.(Kohrt, Malley et al. 1991, Kohrt, Spina et al.

PROTOCOL TITLE: Mild Cognitive Impairment and Endurance Exercise in Parkinson's Disease

1993, Kohrt, Spina et al. 1998) The regimen will include 5-10 min of warm up, 30 min of exercise at target HR and 5-10 min of cool down. They will exercise 3 days per week. The intervention group will be given a HR range to achieve during exercise sessions: 80.0%-85.0% HRmax. During the first 8 weeks of training, exercise duration and intensity will be gradually increased to the target levels. Subjects will be instructed on monitoring HR and adjusting the exercise to remain in the target HR range (i.e., by changing treadmill speed and/or incline). During exercise, subjects will wear a heart rate monitor that captures and stores HR throughout the exercise bout. The exercise Research Assistant (RA) will electronically transfer the HR file from each exercise session (supervised and unsupervised) into the study database.

During the first 2 weeks, subjects must exercise at a main study site under supervision of an Exercise training RA. All 'on-site' exercise sessions will be supervised by an exercise RA. After 2 weeks, the RA will determine whether the subjects may exercise off-site at a community fitness facility or at home to maximize the likelihood of compliance. If the subjects are exercising in their target HR range for the prescribed duration and have demonstrated to the exercise RA that they are able to operate the HR monitor, the subjects will exercise 2X/wk at the main site for 2 weeks and then 1X/wk for 2 weeks. Thereafter, if cleared by the RA, subjects will be expected to exercise on-site at least 1 x/month at the main site. Other exercise sessions will take place at the approved off-site facility. HR monitors must be worn for all sessions. HR data will be downloaded once weekly by an approved person at the facility or brought to a main site to be downloaded by the RA. In addition, the subject will be given an exercise diary log to document his/her wear time sessions on a weekly basis. The RA will check adherence to their prescription each week and will work with the participant as needed to assure appropriate adherence to the protocol.

The intent of allowing exercise off site is to enhance recruitment, retention, and long-term adherence to exercise. Safety with respect to treadmill exercise will be established for each subject during the first two weeks of exercise at the main study site and also has been established in our previous work for 129 subjects with PD, Stages 1.5-3 of H&Y who exercised for up to 6 months without incident ([name], unpublished data). Additionally, many of the designated health clubs we work with are affiliated with hospitals and specialize in exercise programs for people with PD.

The exercise training RA will assure exercise fidelity for each subject by comparing exercise sessions, duration and mean HR to the subject's target on a weekly basis and by working with the subject to make necessary adjustments.

PROTOCOL TITLE: Mild Cognitive Impairment and Endurance Exercise in Parkinson's Disease

An optional online survey administered via email through REDCAP will be sent to participants following completion of the study. The purpose of the online survey is to better understand each subject's experience and satisfaction with the study procedures.

9.3 Procedures performed to lessen the probability or magnitude of risk and source records are described below:

- Minimizing physical, psychological, and social risks: We see no psychological, social, or legal risks beyond those of participation in health-related research in general.
- Minimizing risks to confidentiality: These risks will be minimized by not including personal identifying information on the forms, and by conducting interviews and collection of personal information in a private setting.
- Minimizing risks associated with testing protocol:
 - Clinical assessments: Possible risks associated with clinical evaluations are minimal but may include fatigue, emotional distress, or embarrassment related to some questions on thinking and mood; to minimize these, we will provide breaks in the testing schedule and ask questions in a sensitive, non-judgmental manner.
 - MRI Imaging: All potential participants will be screened for eligibility for a MRI scan as per Radiology guidelines for safety precautions including cardiac pacemaker, metallic implants of any kind in the body, pregnancy, among others. Prior to entering the MRI scan, subjects will be asked again about these safety precautions to determine eligibility for MRI scan. Other possible risks include claustrophobia, boredom, noise, or discomfort from lying supine which will be minimized by talking with the subject periodically during the scanning, providing ear plugs, and providing cushioning. The movement tests are associated with minimal risks, such as stiffness or pain from performing maximal voluntary contractions. This risk will be minimized by providing rest breaks between trials, excluding participants who experience hand pain or other adverse events, and monitoring discomfort. If an individual requires emergency medical care, 911 will be called immediately. This has never happened previously and we have tested more than 100 individuals.
 - Exercise testing: We are using an endurance exercise protocol that we have extensive experience with. Participants are very closely supervised over the first 2 weeks of training to make sure that they are safe and can perform the exercise protocol.
 - Medication withdrawal: All subjects are offered hotel

PROTOCOL TITLE: Mild Cognitive Impairment and Endurance Exercise in Parkinson's Disease

accommodations near the testing facility on the nights prior to testing days during which they are asked to withdrawal from anti-Parkinsonian medication in order to avoid the need to commute to the testing facility while off medication. A research assistant will meet the subjects each morning at the hotel and will accompany the subject via wheelchair, if needed, to the testing facility.

- The risk associated with blood draws are minimal and are reduced in this study because trained personnel who have extensive venipuncture experience, and are trained in aseptic technique, will implement the blood drawing procedures in a clean room.

- No drugs and devices will be used in the research - NA.

- Data collection forms will be used to record the study data and are attached. Forms for test measures are attached for the following tests:
 1. SCOPA-Cog
 2. NINDS Demographics, CDE
 3. MDS UPDRS parts 1,2, 3 (motor) and 4
 4. PD Neurol QOL,
